5. METHODS

5.8 Statistical Analyses

Estimated attrition: Combining armodafinil non-responders and those who decline counseling, we estimate that 80% of patients starting armodafinil treatment will enter counseling. Patients who are self-described as fatigued but who do not meet fatigue criteria will enter counseling without a medication phase, so 100% of these patients should enter counseling.

Estimated effect magnitude of armodafinil plus BA-PEP: In prior trials of modafinil and armodafinil, 27% achieved a specific work or training goal without counseling. In our current study combining armodafinil and counseling, 62% randomized to BA achieved their goal of work or training and 20% of SC patients did so. We expect patients not meeting fatigue criteria to follow the same percentages. We thus conservatively anticipate response rates of 60% for BA patients vs. 25% for SC patients.

5.8.2 Data Management. All research ratings and self-report scales are checked for accuracy and completeness before the patient leaves the clinic, and omissions or inconsistencies addressed. The data are double entered into a PC-based data management system. Data are analyzed using PC-based statistical packages.

Sample size and randomization: We propose to enroll a total of 140 patients (100 who are fatigued, and 40 who self-described as fatigue but do not meet fatigue criteria) seeking treatment to return to work with counseling, and armodafinil for those patients who are fatigued. The randomization will be carried out by the statistician. Individuals will be stratified by fatigue (two levels: those who will be given armodafinil for fatigue, and those who will not be given armodafinil). Stratification will ensure comparable representation of fatigued and non-fatigued patients across the treatment groups. The randomization sequences will be balanced in blocks of random size (2, 4) to prevent clinicians from guessing what the next patient's treatment might be.

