5.8.3: Analytic Strategies. (End points are final study visit and 3-month follow-up visit)

Specific Aim 1: to determine whether more patients in BA-PEP (N=70) return to work or start training compared to SC patients (N=70).

Hypothesis 1: Our primary outcome measure is success in work/training goal attainment using a modified GAS score; we hypothesize that 60% of BA-PEP patients will succeed as compared to 25% of SC patients. BA-PEP will significantly promote success in work goal attainment as compared to SC.

Analysis Plan: The effect of BA-PEP on the primary outcome (work goal attainment) will be examined using a logistic regression (PROC LOGISTIC in SAS[®]) adjusted for appropriate covariates (e.g., stratification variable, depression measure).

Specific Aim 2: Determine whether secondary outcomes, as measured from baseline to the end of treatment, differentiate between BA-PEP and SC. These include the Behavioral Activation Depression Scale, the Environmental Reward Observation Scale (EROS), Endicott Quality of Life, Role Function scale, and Mastery.

Hypothesis 2: Over time, the BA-PEP patients will show significantly more improvement compared to SC patients.

Analysis Plan: Hypothesis 2 will be analyzed using longitudinal mixed effect models (PROC GLIMMIX in SAS[®]) with main effect of time, treatment and interaction between treatment and time effect. The within subjects repeated measure across time will be the baseline session, session 4, and session 8 [end of treatment] assessments for the BADS Scales and the EROS, and the between subjects factor will be the two treatments (i.e. SC and BA-PEP counseling). Demographic measures and other characteristics that are significantly different between the two treatment groups at baseline, will be included as covariates. The main focus of the analysis will be on the interaction term of treatment and time, which addresses treatment group response over time. If the interaction term of treatment and time is found to be significant, we will test the contrast between treatment groups at session 8 [end of treatment].

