Hypothesis 1: 60% of BA-PEP treated patients will attain their goal compared to 25% of the SC treated patients. We will enroll 70 patients into each treatment arm (50 who responded to armodafinil and 20 who self-described as fatigued but did not meet fatigue criteria). With expected rates of 60% and 25% goal attainment, a difference of 35%, power is over 95%. Differences as small as 23% can be detected with 80% power, for reasonable percentages of goal attainment in the SC treated patients, e.g., (48% BA-PEP vs. 25% SC), (53% BA-PEP vs. 30% SC), (63% BA-PEP vs. 40% SC).

Hypothesis 2: We predict that the secondary assessments will distinguish between the two treatment groups with BA-PEP patients showing more improvement by the end of the treatment period compared to SC patients. Using power estimates for three repeated measures (baseline session, session 4, and session 8 [end of treatment]), for 70 patients per group, alpha set at $p < .05$ for a two-tailed test and correlation between repeated measures estimated at .30: (Effect size/Power) .45 [medium]/80%, .48/85%, .52 /90%, .58/95%.

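### Power is computed on 70 counselled patients per arm, but the SAP's own 80% entry rate leaves 60 per arm from the 140 enrolled, so 80% power for a 23-point difference is not delivered

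*SAP*

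**What the plan says.** Three places in the SAP bear on the number of patients who reach counseling.

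- **5.8, Estimated attrition.** Non-responders to armodafinil and patients who decline counseling are combined: "we estimate that 80% of patients starting armodafinil treatment will enter counseling". Patients who do not meet fatigue criteria have no medication phase, "so 100% of these patients should enter counseling".
- **5.8.2, Sample size and randomization.** The enrollment target reads as follows: "We propose to enroll a total of 140 patients (100 who are fatigued, and 40 who self-described as fatigue but do not meet fatigue criteria". The strata are defined by whether the patient is going to be given armodafinil.
- **5.8.3, Specific Aim 1 and Power Considerations.** Aim 1 asks whether "more patients in BA-PEP (N=70) return to work or start training compared to SC patients (N=70". Hypothesis 1 is powered on this basis: "We will enroll 70 patients into each treatment arm (50 who responded to armodafinil and 20 who self-described as fatigued". Two power claims follow: "With expected rates of 60% and 25% goal attainment, a difference of 35%, power is over 95" percent, and "Differences as small as 23% can be detected with 80% power", with 48 vs 25, 53 vs 30 and 63 vs 40 as examples. The Hypothesis 2 power figures also use 70 per group.

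**The concern.** The same 100 fatigued patients are counted before attrition in the enrollment figure and after attrition in the power section. Fifty responders per arm is 100 responders from 100 fatigued enrollees, which implies that every patient responds and accepts counseling. The SAP itself expects one in five not to get that far. The 80% enters no calculation, and no larger number of starters appears in the document.

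The stated sensitivity for both hypotheses therefore rests on 20 patients who, by the plan's own estimate, will not be counselled. A reader also cannot tell whether 140 is the number to enroll or the number to counsel, and those readings differ by about 25 patients.

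**Working it through.** **Inputs from the SAP.** Enrolled: 100 fatigued and 40 not meeting fatigue criteria (5.8.2). Entry to counseling: 80% and 100% (5.8). Equal allocation and the rate pairs are from 5.8.3. Two-sided 0.05 is stated only for Hypothesis 2 and is assumed here for Hypothesis 1.

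**Step 1: number counselled.** 100 × 0.80 + 40 × 1.00 = 120, which is 60 per arm (40 fatigued and 20 not). In reverse, 100 counselled fatigued patients need 100 / 0.80 = 125 starters, and 125 + 40 = 165 enrolled.

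**Step 2: power formula.** Pooled two-proportion z-test, with p̄ the mean of the two rates:

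power = Φ{ [ |p1 − p2| − 1.96 √(2 p̄(1 − p̄)/n) ] / √[ (p1(1 − p1) + p2(1 − p2))/n ] }

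For 48 vs 25, p̄ = 0.365.

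- n = 70: (0.23 − 1.96 × 0.0814) / 0.0790 = 0.892, so power is 81.4%.
- n = 60: (0.23 − 1.96 × 0.0879) / 0.0854 = 0.676, so power is 75.1%.

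**Step 3: all stated pairs.**

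| Rates | Stated | 70 per arm | 60 per arm |
|---|---|---|---|
| 60 vs 25 | over 95% | 99.1% | 98.0% |
| 48 vs 25 | 80% | 81.4% | 75.1% |
| 53 vs 30 | 80% | 79.5% | 73.0% |
| 63 vs 40 | 80% | 78.3% | 71.8% |

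The 70-per-arm column reproduces the SAP's claims to within 2 points, so the SAP's figures are those for 70 per arm with no attrition.

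**Step 4: detectable difference at 80% power.** For control rates of 25, 30 and 40% it is 22.6 to 23.5 points at 70 per arm, and 24.5 to 25.3 points at 60 per arm.

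**Step 5: does the choice of test matter?** At 60 per arm the three 23-point pairs give:

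- unpooled z-test: 76.9, 74.8 and 73.6%
- exact power of the chi-square test: 75.4, 73.8 and 73.4%
- Fisher's exact test: 68.5, 67.2 and 66.9%

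No two-sided variant tried reaches 80%. A one-sided 5% test would (about 82 to 84%), but at 70 per arm it gives about 87 to 89%, which does not match the stated 80%.

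**Step 6: if all 70 per arm are analysed.** Suppose patients who never enter counseling are kept in the analysis as failures, equally in both arms. Each rate is then multiplied by 60/70, and a 23-point difference becomes 23 × 60/70 = 19.7 points. Power for the three pairs is 71.5, 68.7 and 65.4%. For 60 vs 25 it is about 96.6%.

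**Step 7: Hypothesis 2.** The SAP does not give enough detail to rebuild its table; a plain two-sample comparison of means at 70 per group gives 75.9% for an effect of .45, not 80%. I therefore took the stated pairs as given and scaled by √(60/70) = 0.926. For 80% power: (1.960 + 0.842) × 0.926 − 1.960 = 0.634, and Φ(0.634) = 74%. In the same way 85, 90 and 95% become about 79, 85 and 92%. Equivalently, the effects .45, .48, .52 and .58 become .49, .52, .56 and .63 at unchanged power.

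**The case against.** The best defence is that 140 counts patients randomized to counseling after the medication phase. The figure stands in the paragraph on randomization, and 70 + 70, 50 + 50 and 20 + 20 all agree with it. The 80% would then be a run-in yield, the number of starters would be a recruitment figure that may stand in the protocol, and 70 per arm would be right.

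This reading is possible but does not fit the text well. Section 5.8.2 calls 140 the number enrolled and describes the fatigued stratum as patients still to be given the drug, whereas 5.8.3 describes the same number as having responded to it. If the defence is right, the enrollment statement is wrong instead, because about 165 would have to be enrolled. The two passages conflict either way.

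The objection on importance has more force. The trial is planned on 60% versus 25%, and that contrast stays above 95% power even when non-entrants count as failures. What fails is the supplementary detectable-difference claim, by about 2 points, and the Hypothesis 2 figures, by about 8% in effect size. It is also true that the test and alpha for Hypothesis 1 are assumed, and that the calculation in step 6 covers only one of the SAP's three ways of handling dropouts.

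**Conclusion.** The concern holds. As written, the SAP's enrollment and entry rate give 60 counselled patients per arm, not 70. The claim of 80% power for a 23-point difference is then 72 to 75%, with about 25 points detectable at 80%. The Hypothesis 2 powers are each overstated by about 3 to 6 points. The headline claim of over 95% power for 60% versus 25% is unaffected, at 98%.

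This rests on reading 140 as enrollment before armodafinil, on a two-sided 0.05 unadjusted comparison of proportions for Hypothesis 1, and on simple scaling for Hypothesis 2. The contradiction is plain; its practical consequence is moderate.

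**What to change.** State what the 140 counts, and make 5.8, 5.8.2 and 5.8.3 agree.

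- **If 140 is the number enrolled:** use 60 per arm (40 fatigued and 20 not) in Specific Aim 1 and throughout Power Considerations. Restate Hypothesis 1 as 98% power for 60% versus 25%, and 80% power for differences of about 25 points. Rerun the Hypothesis 2 calculation at 60 per group. Give alpha, sidedness and the test for Hypothesis 1. This costs wording only: the stated power is slightly less favourable, and the main hypothesis needs no extra patients.
- **If 140 is the number entering counseling:** keep 70 per arm, say so in 5.8.2, and state that about 125 must start armodafinil and about 165 must be enrolled. This costs about 25 more enrolled patients than the present figure.

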Note #1: We will review baseline sociodemographic, psychiatric, medical history variables, HCV infection and HIV illness stage to determine whether there are significant differences between treatment groups on any relevant measure. If so, each measure will be studied in terms of their relationship to treatment outcome. If related to outcome, they will be entered as covariates in all outcome analyses. To distinguish between depression and fatigue, a depression measure (BDI [67]) will be used as a covariate in all analyses. In addition to standard scoring, the depression measures (BDI and HAM-D [67]) will be adjusted and scores prorated to exclude the fatigue items.

Missing Data. The pattern and distribution of missing data will be examined, and recourse taken to assess randomness and correlates as described in Cohen and Cohen [87, Chapter 7]. Assuming it is randomly distributed, appropriate estimates of missing values will be generated and used in analyses. For AIM 2 the examination of the secondary outcomes across the treatment period (i.e. BADS and EROS Scales), we will be using Linear Mixed Models for analyses. In the presence of missing data, Mixed Models uses all data, estimates parameters and test hypotheses about them but do not impute missing values [88], and Mixed Models can reduce bias due to dropouts [89]. For dichotomous outcomes, secondary

analyses will be performed that use alternative methods of imputation (e.g. last observation brought forward).³

Attrition. We will deal with dropouts in 3 ways: excluding dropouts, counting dropouts as failures, and finally counting dropouts as responders, providing an idea of all possible outcomes are. As noted above, we will use Linear Mixed Models for analyses where appropriate, which can reduce bias due to dropouts.

Data Transformation. We will check all variables in terms of univariate and bivariate distributions to make sure any data analytic method we use appropriately reflects the relationship between the variables-- e.g. we will use nonlinear transformations and polynomial regression as necessary.

Definition of primary dependent variables:

Work: paid employment: 4+ hours/week including stipend jobs; volunteer work; Increased work hours: at least 20% increase with a minimum increase of 4 hours/week.

Training: Includes enrollment in GED classes, degree and vocational programs, computer classes, unpaid or stipend internships.

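### The Hypothesis 2 power row names neither its effect-size scale nor its test; if .45 is a session-8 difference in raw SDs, the planned interaction has about 50–63% power, not 80%

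*SAP*

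**What the plan says.** SAP section 5.8.3, Power Considerations, Hypothesis 2, predicts "BA-PEP patients showing more improvement by the end of the treatment period compared to SC patients". The basis is given as "Using power estimates for three repeated measures (baseline session, session 4, and session 8 [end of treatment]), for 70 patients per group", with two-tailed alpha of .05, and then the row itself: "correlation between repeated measures estimated at .30: (Effect size/Power) .45 [medium]/80%, .48/85%, .52 /90%, .58/95" percent. No SD, visit or contrast is attached to the effect size, no correlation structure is given, and no test is named.

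The Aim 2 analysis plan in the same section specifies a longitudinal mixed model with treatment, time and their interaction over baseline, session 4 and session 8, for the "assessments for the BADS Scales and the EROS". It states: "The main focus of the analysis will be on the interaction term of treatment and time". The session-8 comparison is conditional: "If the interaction term of treatment and time is found to be significant, we will test the contrast between treatment groups at session 8". The plan does not say whether time is categorical (2 df) or linear (1 df). Baseline is one of the repeated outcomes. It is neither constrained to a common mean nor entered as a covariate.

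**The concern.** A reader will take the row as 80% power to show an end-of-treatment difference of .45 SD with the planned analysis. That holds only if the row was computed for the planned test and on that scale. An interaction with free baseline means spends information on estimating a baseline difference that randomisation makes zero in expectation. In the same units it is therefore weaker than a baseline-adjusted comparison at session 8. If the row belongs to the latter, Aim 2 is much less well powered than it appears. When the interaction misses significance, the end-of-treatment contrast is not tested at all.

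**Working it through.** **Inputs from the SAP:** 70 per arm, two-sided alpha .05, correlation .30, three visits, effects .45/.48/.52/.58. **Assumptions, not in the SAP:** compound symmetry, no dropout, equal true baseline means, outcome SD 1 at each visit. d is the session-8 difference in those SDs. The course of the effect is also not given, so three are used: linear (0, d/2, d), full by session 4 (0, d, d), and only at session 8 (0, 0, d).

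**1. Reproducing the row.** Adjusting session 8 for baseline leaves variance 1 − .30² = .91. Inverting the normal approximation, d = (1.96 + z)·√(.91/35), gives .452, .483, .523 and .581 for 80, 85, 90 and 95% power. These round to all four printed values. Using the t distribution with 137 df, the noncentrality at .45 is .45·√(35/.91) = 2.79 and power is 79.1%.

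**2. The planned interaction in the same units.**
- 2 df: noncentrality 35·SS/(1 − .30), with SS the sum of squared deviations of the three differences from their mean, tested against F(2, 276). Linear: SS = d²/2, so at .45 it is 35 × .10125/.7 = 5.06. The other two courses: SS = 2d²/3, so 35 × .135/.7 = 6.75.
- 1 df: change from baseline to session 8, variance 2(1 − .30) = 1.4, noncentrality .45·√(35/1.4) = 2.25.

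| Power (%) at d = | .45 | .48 | .52 | .58 |
|---|---|---|---|---|
| SAP row | 80 | 85 | 90 | 95 |
| Session 8, baseline-adjusted | 79.1 | 84.0 | 89.3 | 94.6 |
| Interaction, 2 df, linear | 50.4 | 56.1 | 63.4 | 73.5 |
| Interaction, 2 df, other two courses | 63.3 | 69.4 | 76.7 | 85.6 |
| Interaction, 1 df | 60.8 | 66.4 | 73.3 | 82.1 |

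**3. The planned sequence** (2-df interaction significant, then session 8 significant; simulated at .45): 45% linear, 51% full by session 4, 57% late. With a baseline-adjusted session-8 contrast: 48, 56 and 60%. With no true effect, the sequence declares a session-8 difference in about 1.1% of runs (1.7% if adjusted).

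**4. Other readings that fit the row.**
- 2-df interaction with SS = d², the interaction's own scale: noncentrality 35 × .2025/.7 = 10.1, power 81.6/86.5/91.6/96.3%.
- 2-df interaction with the effect in SDs of change, full by session 4 or late: .45 then means .45·√1.4 = .53 raw SD, power 78.7/84.0/89.6/95.1%.
- Normalised linear contrast under AR(1): variance (2 − 2 × .09)/2 = .91, so the row is again reproduced, and .45 means .45·√2 = .64 raw SD.

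**5. The same model with baseline handled as common.** Adjusted for baseline, the differences at sessions 4 and 8 have covariance (1/35) × [.91, .21; .21, .91], since .30 − .09 = .21 and the determinant is .91² − .21² = .784. The joint 2-df noncentrality is 35 times the quadratic form in the inverse. At .45:
- linear: 35 × .1878/.784 = 8.4, power 73%;
- full by session 4: 35 × .2025 × 1.4/.784 = 12.7, power 89%;
- late: 35 × .2025 × .91/.784 = 8.2, power 72%.

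Requiring this test and then the adjusted session-8 contrast gives about 70–77%. The false-positive rate of that sequence is about 2% per scale (2.5% in a check of 100,000 simulated trials).

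**The case against.** The strongest reply is that the row may be right. On each reading in step 4 the row is the power of an interaction test, and nothing in the SAP excludes them. That stands: a reader might infer a calculation error, and the document does not support one.

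A reader might also infer that the gate costs a fixed, large amount of power whichever reading applies. That does not hold. On the interaction-scale reading at .45, a late effect gives 90% for an ungated session-8 test and 78% for the sequence, about 12 points; losses are smaller at .58. On the interaction-type readings the comparison is also with an ungated test that the SAP never promised: measured against the printed 80%, the sequence gives about 71–81%. Part of any such gap is simply a 5% test set against a sequence with about 1% false positives. For raw-SD effects, an unadjusted session-8 test run at 1.1% has about 54% power, against 45–57% for the gated sequence. Removing the gate is therefore a trade-off, and requiring an interaction before a follow-up contrast is a conventional procedure.

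Two further points are fair. Hypothesis 2 is worded as improvement over time, which the interaction does address. And SAP section 5.8.2, Note #1, makes the BDI a covariate in all analyses, which may reduce residual variance; no figure is given, so the gain cannot be sized. Neither point supplies the missing definition of the effect size and test.

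**Conclusion.** The point holds as an undefined effect size and a probable mismatch between the powered test and the planned one. The simplest test that fits the row, with the effect in ordinary SDs, is a baseline-adjusted session-8 comparison that the Aim 2 plan does not contain. If that is what was meant, power at .45 is about 50–63% (2 df) or 61% (1 df) for the interaction and 45–57% for the sequence (48–60% with an adjusted session-8 contrast). At .58 the 2-df interaction has about 74–86%, not 95%.

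These figures rest on compound symmetry .30, no dropout, equal true baseline means and the three courses shown. On the other fitting readings the row describes an interaction test, but .45 then stands for a larger raw difference, for example .53 or .64 SD. Only secondary Aim 2 is affected. This should be fixed, but it does not threaten the primary result.

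**What to change.** **Aim 2 analysis plan.** Fit the model with a common baseline mean for the two arms, or enter the scale's baseline score as covariate with sessions 4 and 8 as outcomes. In either form the gate should be the joint 2-df test of the adjusted treatment differences at sessions 4 and 8. With baseline as covariate, the interaction term alone would only compare session 4 with session 8. Use the adjusted contrast at session 8. State whether time is categorical.

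**Power paragraph.** Give the effect size in session-8 SDs, the correlation structure, the assumed course of the effect and the test powered, and recompute the row for that test. The values 79/84/89/95% apply only to an ungated, baseline-adjusted session-8 contrast with correlation .30.

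**Optional.** Make that contrast the Aim 2 test without a gate. Per-scale false positives then rise from about 1–2% to 5%. For the two scales in the three-visit model, taken as independent, that is 1 − .95² = 9.75% overall. So name one key scale, or test each at .025 (about 70% power at .45 raw SD).

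**Cost.** SAP wording and a small change to the GLIMMIX code; no new data or visits. The main change keeps the gate and raises its per-scale false-positive rate only slightly, from 1–2% to about 2%.
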